4.1.2 Part 1B: Single Ascending Dose of MGD020 and Fixed-Dose of MGD014

Part 1B commences only after the MTD or MAD of single-agent MGD020 has been determined in Part 1A. During Part 1B, participants will be enrolled and treated with a single ascending dose of MGD020 in combination with a fixed dose of 300 mcg/kg MGD014.

MGD020 and MGD014 will be administered at the doses shown in **Table 2** using a 3+3 design, beginning with Cohort 1, with at least 72 hours between dosing of each participant within a cohort. The first cohort will be treated with a single dose of MGD020 at a dose determined to be one dose level lower than the MTD/MAD from Part 1A (i.e., one dose level lower than MTD_{1A}/MAD_{1A}). MGD014 is dosed at 300 mcg/kg, as determined from Study CP-MGD014-01.

In Part 1A, the MGD020 dose is increased in half-log increments from 1 to a maximum of 300 mcg/kg. In Part 1B, the maximum starting dose of MGD020 for Cohort 1 of Part 1B will thus be 100 mcg/kg (one dose level below the Cohort 6 dose of 300 mcg/kg). In combination with MGD014 at 300 mcg/kg, this would yield a maximum total DART dose of 400 mcg/kg for Cohort 1 of Part 1B, which is less than a half-log increment over the total DART dose that would have been tolerated in Part 1A.

Escalation to the next cohort follows the rules described in **Section 4.2**.

Table 2 MGD020 and MGD014 Combination Dose Escalation Scheme (Part 1B)

Cohort	MGD020 ^a (mcg/kg)	MGD014 (mcg/kg)	Design
-1 ^b	MGD020 MTD _{1A} /MAD _{1A} -2	300	3+3
1	MGD020 MTD _{1A} /MAD _{1A} -1	300	3+3
2	MGD020 MTD _{1A} /MAD _{1A}	300	3+3

- a Dosing for Part 1B will begin with Cohort 1. The MGD020 dose in Cohort 1 will be one dose level below the single-agent MTD/MAD in Part 1A. For example, if the MTD/MAD in Part 1A for MGD020 is 300 mcg/kg, Cohort 1 of Part 1B would receive 100 mcg/kg MGD020 + 300 mcg/kg MGD014.
- b If the dose level in Part 1B Cohort 1 exceeds the MTD, de-escalation to Cohort -1 may be considered. For example, if MTD is exceeded when the Part 1B Cohort 1 dose is 100 mcg/kg MGD020 + 300 mcg/kg MGD014, Cohort -1 of Part 1B would receive 30 mcg/kg MGD020 (MTD_{1A}/MAD_{1A} -2 dose from Part 1A) + 300 mcg/kg MGD014.

Participants who completed Part 1A may be considered for enrollment in Part 1B, provided they meet all eligibility criteria, did not experience DLT in Part 1A, and do not have detectable ADA against MGD014 and/or MGD020 at the completion of Part 1A.

4.1.3 Part 2: Multi-Dose Expansion Cohort: Fixed-Dose of MGD020 and Fixed-Dose of MGD014

Part 2 commences only after an MTD or MAD of MGD020 in combination with MGD014 has been determined in Part 1B. Part 2 is a multi-dose expansion cohort with sequential infusions of a fixed dose of MGD020 in combination with a fixed dose of MGD014 administered Q2W for 3 combination doses over 4 weeks (**Table 3**). MGD020 is dosed at the MTD/MAD determined in Part 1B (i.e., MTD_{1B}/MAD_{1B}). MGD014 is dosed at 300 mcg/kg, as determined from Study CP-MGD014-01.

Up to 6 participants may be enrolled in Part 2 using a conventional 3+3 design. If 2 or more participants in the cohort of 6 participants experience a DLT, enrollment and further dosing of ongoing participants will be suspended pending further assessment of safety data.

Table 3 MGD020 and MGD014 Combination Multi-Dose Expansion Cohort Scheme (Part 2)

Cohort	MGD020 ^a (mcg/kg)	MGD014 (mcg/kg)	Design
1	MGD020 MTD _{1B} /MAD _{1B}	300	3+3

- a The MGD020 dose is determined by the combination MTD or MAD in Part 1B.

Participants who completed Part 1 may be considered for enrollment in Part 2, provided they meet all eligibility criteria, did not experience DLT in Part 1, and do not have detectable ADA against MGD014 and/or MGD020 at the completion of Part 1.

4.2 Dose Escalation Rules

Dose escalation from one dose cohort to the next higher dose cohort depends upon the clinical safety profile (e.g., evaluation of AEs, vital signs, ECGs, and clinical laboratory parameters) of the dose administered up to and including the preceding dose cohort. Dose escalation to the next dose level is permitted only after the participants enrolled in the current dose cohort have completed the DLT evaluation period and the safety data have been reviewed by the sponsor medical monitor and the study investigators. Evaluation of safety data from each cohort will include an assessment of the proportion of participants who receive planned doses, and the percentage of participants that require dose reductions or dose discontinuations for toxicity. Available data from participants both during and beyond the 2-week DLT evaluation period will be considered when making dose escalation decisions.

Dose escalation continues until all cohorts are enrolled, provided the MTD is not exceeded. If 2 or more of the participants in a dose cohort experience a DLT, the MTD will have been exceeded. If a DLT occurs in 1 participant in a dose cohort, the dose cohort will be expanded to an additional 3 participants. Prior to dosing any additional participants at the same dose, study drug safety and tolerability are evaluated over the entire 2-week DLT period for the first additional participant.

If the first additional participant does not experience a DLT during the DLT period, the 2 other additional participants can proceed to receive study drug at this dose with a minimum of 24 hours between dosing of each participant. If none of the 3 additional participants experience a DLT during the DLT period, dose escalation to the next dose cohort may proceed.

If any of the 3 additional participants experiences a DLT during the DLT period (≥ 2 DLTs within the same dose cohort), no further participants will receive a dose at this dose level, as the MTD will have been exceeded. Part 1B then proceeds at one dose level below the single-agent MTD_{1A}/MAD_{1A} of MGD020 determined in Part 1A. If only 1 participant was enrolled at the prior dose level in Part 1A, an additional 3 participants will be enrolled at the prior dose for evaluation of the MTD/MAD.

Participants who do not complete the DLT period for reasons other than study drug-related toxicity may be replaced in the same dose cohort. At the discretion of the sponsor, dose escalation may be stopped before an MTD is reached. In this case, the MAD may be chosen based on an assessment of PK, pharmacodynamics (PD), and safety data. For example, dose escalation may be stopped if study drug binding to CD3⁺ T cells exceeds 95% within a dose cohort.

4.3 Dose-Limiting Toxicity

DLT is defined based on treatment-related AEs that occur during the DLT period following study drug administration. The DLT period is defined as the period from initial infusion of study drug(s) through 2 weeks following the last study drug infusion.

Severity of AEs is graded according to the National Institute of Allergy and Infectious Diseases (NIAID) Division of Acquired Immunodeficiency Syndrome (DAIDS) Table for Grading the Severity of Adult and Pediatric Adverse Events, corrected version 2.1, July 2017 (see [Section 12.1.6](#)).

A DLT is any \geq Grade 2 treatment-related AE, with the following exceptions, based on the medical judgement of the investigator (or designee) and medical monitor:

- Grade 2 laboratory abnormality that lasts $<$ 72 hours and is not otherwise associated with clinical complications.
- Grade 2 fatigue that lasts $<$ 7 days.

4.4 Guidelines for Dose Modification

No dose modifications are allowed. A reduction of the infusion rate is allowed during re-challenge for an infusion reaction ([Section 7.1](#)).

4.4.1 Dose Delays

Hold study drug administration for toxicity, pending assessment, management, and resolution of the AE. If the AE is assessed as unrelated to study drug(s) or does not meet DLT criteria, study drug(s) may be restarted at the previous dose and schedule, after appropriate recovery.

In Part 2, a dose delay of up to 7 days is allowed for drug-related or non-drug related AEs. Refer to [Section 7.1](#) for specific guidance on restarting study therapy after infusion reactions. A dose delay $>$ 7 days due to drug-related toxicity will prompt study drug discontinuation.

4.5 Study Drug Discontinuation

Administration of study drug(s) may continue as specified in the protocol until any of the following conditions are met:

- Adverse event requiring study drug discontinuation (including DLT)
- Completed dosing per protocol
- Death
- Lost to follow-up
- Investigator decision
- Pregnancy
- Major protocol deviation requiring study drug discontinuation
- Study terminated
- Participant decided to discontinue study drug

- Participant withdrew consent from study

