7.1.1 Grading and Management of Infusion Reactions

Infusion reactions and CRS will be graded according to the criteria in the DAIDS Table for Grading the Severity of Adult and Pediatric Adverse Events, corrected version 2.1, July 2017.

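### A related Grade 2 or 3 infusion reaction meets the DLT definition, and Protocol 4.5 lists DLT among the events that end study drug, yet 7.1.3 allows further dosing with no written exception

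*Protocol*

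**What the plan says.** **What counts as a DLT.** Protocol 4.3 sets the threshold at or above "Grade 2 treatment-related AE, with the following exceptions, based on the medical judgement of the investigator (or designee) and medical monitor". Two exceptions follow: a short-lived Grade 2 laboratory abnormality without clinical complications, and short-lived Grade 2 fatigue. On timing: "The DLT period is defined as the period from initial infusion of study drug(s) through 2 weeks following the last study drug infusion". Section 7.1.1 uses the same severity scale for infusion reactions: "Infusion reactions and CRS will be graded according to the criteria in the DAIDS Table".

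**What a DLT does to dosing.** Section 4.5 lists the conditions that end study drug. One entry reads "Adverse event requiring study drug discontinuation (including DLT". Section 4.4.1 says that after a hold, if the event is unrelated "or does not meet DLT criteria, study drug(s) may be restarted at the previous dose and schedule". A participant may move from Part 1 to Part 2 "provided they meet all eligibility criteria, did not experience DLT in Part 1".

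**What the infusion-reaction section does.** Section 7.1.3 presents suggested guidance that the investigator may modify. After a Grade 2 reaction it resumes the infusion at a reduced rate and foresees later infusions. If symptoms return, it stops drug for that visit. After a Grade 3 reaction it stops drug for that visit but permits a restart at the next scheduled dose if symptoms clear fully within 12 hours. It calls for permanent discontinuation only at Grade 4. Section 7.1.2 permits a steroid to be added to the premedication after a first-infusion reaction of Grade 2 or higher, which presumes another infusion.

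**Links between the two.** Section 4.4 states: "A reduction of the infusion rate is allowed during re-challenge for an infusion reaction", and cites 7.1. Section 4.4.1 also sends the reader to 7.1 for restarting after an infusion reaction. The SAP does not address the question.

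**The concern.** Two safety instructions seem to answer one question differently: may a participant whose infusion reaction is a DLT receive more study drug? MGD020 is first-in-human (2.3.1.1), infusion reaction and cytokine release syndrome are named potential risks (2.5.1), and the synopsis plans 3 to 5 institutions. Two sites facing the same reaction could act differently, one stopping under 4.5 and the other re-dosing under 7.1.3, each with protocol text behind it.

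The primary endpoint in 3.1 includes adverse events leading to discontinuation. The effect there is indirect. Section 12.2.1 has the action taken recorded for every event, so the endpoint will report what was done, but what was done would depend on which section the site followed.

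**Working it through.** **Step 1: is the reaction a DLT?** Inputs are 4.3 and 7.1.1. A related Grade 2 or 3 infusion reaction is at or above the threshold, is graded on the same scale, and is neither a laboratory abnormality nor fatigue. The DLT period runs to 2 weeks after the last infusion, so every Part 2 infusion lies inside it. The answer is yes.

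**Step 2: the rules side by side, for a related reaction.**

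| Grade | 4.3 | 4.5, plain reading | 7.1.3 |
|---|---|---|---|
| 1 | not a DLT | no stop | slow the infusion; continuing allowed |
| 2 | DLT | study drug ends | resume at reduced rate; later infusions foreseen |
| 3 | DLT | study drug ends | none that visit; next scheduled dose allowed after full resolution within 12 hours |
| 4 | DLT | study drug ends | permanent stop |

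The sections agree at Grades 1 and 4 and part at Grades 2 and 3.

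**Step 3: where later doses exist.** Under 6.1, Part 1A gives one dose of MGD020 and Part 1B one combination dose. Only Part 2 has later doses, so the later-dose conflict is confined to Part 2.

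**Step 4: further whole infusions in Part 2.** There are 3 dosing visits and 2 drugs, with MGD020 first: 3 × 2 = 6 planned infusions. Let the reaction occur in infusion k, at visit v = k/2 rounded up.

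- 4.5, plain reading: 0 for every k.
- 7.1.3, Grade 2 without recurrence: at most 6 − k. For k = 1, 6 − 1 = 5.
- 7.1.3, Grade 3 resolved in time: at most 2 × (3 − v). For k = 1, v = 1, so 2 × 2 = 4.

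| Infusion k | 1 | 2 | 3 | 4 | 5 | 6 |
|---|---|---|---|---|---|---|
| 4.5 | 0 | 0 | 0 | 0 | 0 | 0 |
| 7.1.3, Grade 2 | 5 | 4 | 3 | 2 | 1 | 0 |
| 7.1.3, Grade 3 | 4 | 4 | 2 | 2 | 0 | 0 |

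Of the 5 at k = 1, one is the same-day MGD014 infusion, which 7.1.3 permits only by not barring it. The other 4 fall at later visits.

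**Step 5: how many participants before another rule acts?** Section 4.1.3 says: "If 2 or more participants in the cohort of 6 participants experience a DLT, enrollment and further dosing of ongoing participants will be suspended". Section 14.9 also suspends dosing, for independent review, once two participants in any part have a related toxicity of Grade 3 or higher, or the same related toxicity of Grade 2 or higher. Neither rule settles the first participant's case. From the second qualifying case on, dosing stops pending review.

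**The case against.** The strongest reply is that the protocol routes this case to 7.1. Sections 4.4 and 4.4.1 both refer there, 4.4 speaks of re-challenge, and 4.5 opens by letting dosing proceed as the protocol specifies, which includes 7.1. The entry in 4.5 could also cover only those DLTs judged to require discontinuation. On that view there is a general rule, a specific rule, and a missing linking clause.

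Much of this stands. An exception may well be intended, and 4.4.1 supports a bar on restart only by implication: it says when restart is allowed, not that it is otherwise forbidden. But no exception is written in 4.3 or 4.5, and 7.1 does not mention DLT. The pointers to 7.1 also have a use without overriding 4.5, since Grade 1 reactions are not DLTs. If only some DLTs end study drug, nothing in 4.5 says which.

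Four stronger readings are tempting, and the documents do not support them:

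- *Sites are forced into a breach.* Section 7.1.3 is modifiable and its Grade 3 restart is optional. A site that stops under 4.5 breaches nothing; the conflict bites only when a site re-doses.
- *All 6 Part 2 participants, or 18 + 6 = 24 places in Parts 1B and 2, are exposed.* The suspension rules intervene at the second case. Part 1B can use at most two of its three cohorts (Cohort 1, then either 2 or −1), so 18 is a planning figure that cannot be reached: 2 × 6 = 12 places before replacements. The same-day second-drug case also rests on silence in 7.1.3.
- *Barring entry to Part 2 after a Part 1 DLT proves the contradiction.* A re-entry criterion may be stricter than guidance for someone already on treatment.
- *The MTD decisions are compromised.* The reaction counts as a DLT whichever section governs re-dosing.

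**Conclusion.** The point holds at Grades 2 and 3. On its plain reading 4.5 ends study drug for a participant whose infusion reaction is a DLT, 7.1.3 allows more, and the exception that would reconcile them is not written.

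The size is 0 against up to 5 (Grade 2 without recurrence) or up to 4 (Grade 3) further infusions after a reaction in the first Part 2 infusion. It concerns mainly the first affected participant, unless dosing resumes after a suspension review. Whether 4.5 also stops completion of an interrupted infusion, which could arise in any part, cannot be settled from the text and is not counted.

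This rests on three assumptions: the reaction is judged related, 4.5 is read as ending study drug for any DLT, and no other reason stops dosing. The frequency is unknown. There are no human data on MGD020, and 2.4.3 reports no infusion reaction or cytokine release syndrome with MGD014. The point still merits correction, because it is a participant-level safety instruction in a first-in-human trial and covers a risk the protocol itself names.

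**What to change.** Reconcile Protocol 4.3, 4.4.1, 4.5, 7.1.2 and 7.1.3. State in one place whether a participant whose infusion reaction meets the DLT definition may receive further study drug, answering separately for:

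- the rest of the interrupted infusion,
- the second drug on the same day,
- later scheduled doses.

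Then make the other sections match or refer to that statement. Which rule applies is a clinical decision for the sponsor and medical monitor; this review takes no position on it.

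The cost is a protocol amendment to wording, with no added participants or procedures.

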4.6 Follow-Up

In Part 1A and Part 1B, after completion of study drug dosing, participants enter the follow-up period, i.e., visits 2 through 7, per the schedule in [Appendix 1](#).

In Part 2, after study drug discontinuation or completion of all 3 combination doses, participants enter the follow-up period, i.e., visits 7 through 9, per the schedule in [Appendix 1](#), if feasible. Visit 7 should be scheduled approximately 14 days after study drug discontinuation. Additional and/or more frequent safety laboratory tests may be performed as clinically indicated per the investigator's discretion.

In all study parts, if a participant is unable to complete the study but has not withdrawn consent, the EOSV (i.e., visit 8 in Part 1A and Part 1B, and visit 10 in Part 2) is conducted 30 days (+3 day window) after the last dose of study drug.

Participants may be classified as lost to follow-up after both of the following criteria are met:

- Failure of participant to respond or reply to 3 documented phone or electronic mail contact attempts.
- Failure of participant to respond to a certified letter.

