4 STUDY DESIGN

4.1 Overall Study Design

Study CP-MGD020-01 is a phase 1, open-label, dose-escalation, and multi-dose expansion study of MGD020 as a single agent or in combination with MGD014 in PWH on ART. The study is designed to characterize the safety, tolerability, PK, immunogenicity, and PD of the study drugs. The study consists of 3 parts (Part 1A, Part 1B, and Part 2). In all parts, the participant's standard of care ART regimen is continued throughout the study period.

Part 1A evaluates single ascending doses of MGD020, Part 1B evaluates single ascending doses of MGD020 in combination with fixed-dose MGD014, and Part 2 is a multi-dose expansion cohort with sequential administration of combination MGD020 and MGD014 Q2W for 3 combination doses over 4 weeks.

The study consists of a screening phase of up to 8 weeks, and an approximately 6-week (Part 1A and Part 1B) or 11-week (Part 2) study period (dosing and follow-up), which concludes with an end of study visit (EOSV) approximately 6 weeks (Part 1A and Part 1B) or 7 weeks (Part 2) after the last dose of study drug. Thus, the total study duration for each participant is approximately 14 weeks (Part 1A and Part 1B) or 19 weeks (Part 2). If a participant is unable to complete the study, but has not withdrawn consent, the EOSV is conducted 30 days (+3 day window) after the last dose of study drug.

An independent safety monitor will provide study oversight and evaluate cumulative safety and other clinical data at regular intervals as described in [Section 14.9](#).

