- Consider IV fluids, supplemental oxygen, and bronchodilators as appropriate.
- The participant may restart study drug(s) at the next scheduled dose if symptoms have completely resolved within 12 hours. A 50% infusion rate reduction is required.

Grade 4:

- STOP THE INFUSION AND DISCONNECT THE INFUSION TUBING FROM THE PARTICIPANT. NO FURTHER STUDY DRUG SHOULD BE ADMINISTERED.
- TO AVOID EXACERBATION OF INFUSION REACTION OR CRS: DO NOT FLUSH THE TUBING – ASPIRATE RESIDUAL DRUG FROM THE VASCULAR ACCESS DEVICE.
- Administer diphenhydramine hydrochloride 50 mg IV, dexamethasone 20 mg IV (or higher doses of steroids, e.g., methylprednisolone 2–4 mg/kg IV or equivalent, as appropriate) and other medications/treatment as medically indicated.
- Consider administering tocilizumab (an IL-6 receptor inhibitor) 4–8 mg/kg IV, in the absence of colitis.
- Give epinephrine or bronchodilators as indicated.
- Support ventilation and blood pressure as indicated.
- Permanently discontinue study drug(s).

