- e On dosing visits (Day 1, 15, and 29), vital signs are measured pre-infusion; at 15 and 30 min after start of infusion (± 5 min); at end of infusion (EOI) of all study drug(s) (± 5 min); at 15, 30, 45, and 60 min post-infusion of last study drug (± 5 min); then every 60 min (± 10 min) until 6 hours after EOI or until the end of the monitoring period (see [Section 6.5.1](#)), whichever comes first (until 2 hours after EOI on Day 15 and 29). During non-dosing in-person visits, vital signs are assessed once.
- f ECGs are performed in triplicate (approximately 1 min apart). At screening and EOSV, ECGs will be taken at one time point. On dosing visits (Day 1, 15, and 29), ECG is recorded pre-infusion, at EOI of all study drug(s), at 30 and 60 min after EOI of last study drug, and as clinically indicated. ECGs after EOI have ± 10 min window.
- g Assess participants for adverse events. Participants are also instructed to contact the study coordinator or investigator if any signs or symptoms of an AE occur at any time during the study.
- h Optional leukapheresis is performed only after the participant is enrolled in the study. If the participant consents to this optional procedure, a baseline leukapheresis is completed. If a baseline leukapheresis was performed, a second leukapheresis procedure is completed 2 weeks (+2 week window) following the final study drug infusion.
- i Additional and/or more frequent safety laboratory tests may be performed as clinically indicated per the investigator's discretion.
- j Clinical laboratory assessments scheduled for Day 1 can be obtained within 7 days prior to infusion. See [Section 9.11](#) for detailed list of assessments. Indirect bilirubin is required if participant on atazanavir.
- k Day 43 hematology is assessed only for participants undergoing leukapheresis. This hematology assessment is performed within the window for the scheduled leukapheresis.

- 1 Participants of childbearing potential only. Serum pregnancy test is required at screening. Subsequent pregnancy tests may use serum or urine. Results must be reviewed before study drug infusion on Day 1, Day 15, and Day 29. If screening test is performed within 72 hours of first infusion, repeat testing on Day 1 may be deferred.
 - m Reflex HCV PCR viral load test is performed only if positive for HCV antibody.

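### Section 4.6 does not keep the post-dose visits and samples already listed for a dose given when a Part 2 participant stops study drug early, so scheduled safety, cytokine and ADA data thin out inside the DLT window.

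*Protocol*

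**What the plan says.** Protocol 4.6 sets the Part 2 route after dosing ends: "after study drug discontinuation or completion of all 3 combination doses, participants enter the follow-up period, i.e., visits 7 through 9", following Appendix 1 where feasible. It continues: "Visit 7 should be scheduled approximately 14 days after study drug discontinuation". For Part 1A and 1B the same section defines follow-up as Visits 2 to 7, which begins on Day 2.

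Table 8 divides the Part 2 calendar differently. Visits 1-6 (Days 1, 2, 4, 8, 15, 29) form the dosing period, Visits 7-9 (Days 43, 50, 64) the follow-up period, and Visit 10 (Day 78) is the end-of-study visit (EOSV). Chemistry falls on Days 1, 15, 29 and 78. Hematology follows the same days plus Visit 7, with a restriction: "Day 43 hematology is assessed only for participants undergoing leukapheresis".

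Protocol 4.3 states: "The DLT period is defined as the period from initial infusion of study drug(s) through 2 weeks following the last study drug infusion". Section 4.5 lists an adverse event, including a DLT, among the reasons for stopping, and 7.1.3 ends dosing permanently after a Grade 4 infusion reaction. A stop on Day 1 is therefore possible.

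On extra tests, 4.6 says: "Additional and/or more frequent safety laboratory tests may be performed as clinically indicated per the investigator's discretion".

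**The concern.** The early post-dose visits in Part 2 are labelled as dosing-period visits, although Days 2, 4 and 8 carry no infusion. Their purpose is to observe the dose just given. A rule that sends a stopper straight to Visit 7 bypasses them, and the participants affected include those who stopped because of toxicity.

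Three things are at stake.

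- **DLT ascertainment.** A related Grade 2 laboratory abnormality counts as a DLT unless it lasts under 72 hours without clinical complications, so finding one depends on laboratory draws. A participant stopped for a DLT is already counted. One stopped for another reason (investigator or participant decision, pregnancy, protocol deviation, COVID-19) is still in an open DLT window, and that result feeds the rule in 4.1.3 that suspends dosing at two or more DLTs among six.
- **Early reactions.** Section 2.4.3 says infusion reactions and cytokine release can appear up to 24 hours after infusion. On-site monitoring after the first Part 2 infusion is 6 hours (12 in Part 1), and Day 2 is the next scheduled contact.
- **Secondary endpoints.** Cytokines, PK and ADA are secondary endpoints, and SAP 4.2 leaves missing data missing. With at most six participants, one stopper is at least one-sixth of the cohort, and later summaries lean towards those who tolerated the drug.

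**Working it through.** **Inputs.** Visit days and laboratory rows: Table 8. Sampling rows: Table 11. Visit 7 timing and the 30-day (+3) early EOSV: Protocol 4.6. EOSV timing: Protocol 4.1, "or 7 weeks (Part 2) after the last dose of study drug". DLT window: Protocol 4.3.

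**Step 1: reproduce the plan's own intervals.** Measured from the last planned dose on Day 29:
- Visit 7: 43 - 29 = 14 days
- Visit 8: 50 - 29 = 21 days
- Visit 9: 64 - 29 = 35 days
- EOSV: 78 - 29 = 49 days = 7 weeks

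These match the 14 days in 4.6 and the 7 weeks in 4.1.

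**Step 2: apply them to a participant whose only dose is on Day 1.** Assumption: Visits 8-10 keep the same spacing.
- Visit 7: 1 + 14 = about Day 15
- Visit 8: 1 + 21 = about Day 22
- Visit 9: 1 + 35 = about Day 36
- EOSV: 1 + 49 = about Day 50, or Day 31-34 (1 + 30 to 1 + 33) if the early EOSV is used
- The DLT window closes at 1 + 14 = Day 15

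**Step 3: count what is scheduled after Day 1 dosing.**

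| Scheduled item | Continues | Stopped on Day 1 |
|---|---|---|
| Visits, Days 2-14 | 3 (Days 2, 4, 8) | 0 |
| Visits, Days 2-15 | 4 | 1 (Visit 7) |
| Visits, Days 2-29 | 5 | 2 |
| Visits, to EOSV | 9 | 4 |
| Cytokine/T-cell rows, through pre-dose Day 15 | 5 (1 h, 4 h, Day 2, Day 8, Day 15) | 2 (1 h, 4 h) |
| On-study ADA samples | 3 (Days 15, 29, EOSV) | 1 (EOSV) |
| Chemistry | Days 15, 29, 78 | EOSV only |

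Time from dose to next scheduled chemistry: 31 - 1 = 30 days with the early EOSV, 50 - 1 = 49 days otherwise.

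Visit 7 keeps a PK sample, so PK loses Days 2, 4 and 8 but not the point at about Day 15. Cytokine, T-cell and ADA samples are absent from the Day 43 row of Table 11.

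**Step 4: stop following dose 2, decided on Day 15.** Visits 2-5 have been made. Visit 7 falls at 15 + 14 = about Day 29, when Visit 6 was due, but without the Day 29 chemistry, routine hematology, cytokine/T-cell and ADA draws. Those laboratory tests are the first scheduled after dose 2. The next chemistry is the EOSV at 15 + 49 = about Day 64, or from 15 + 30 = Day 45 if early.

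The laboratory counts depend on column positions in Table 8, which were read from a text copy of the PDF. Footnotes j and k agree with that reading.

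**The case against.** The strongest reply is that the loss is inferred from silence. Section 4.6 does not cancel Visits 2-4, and a site might keep them. That is fair as a prediction of practice, but the section names the visits that follow a stop, and for Part 1 it names the early ones explicitly.

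Second, many stops would not be decided on Day 1. Section 4.4.1 holds drug while an event is assessed, the DLT exceptions turn on 72 hours and 7 days, a resolved Grade 3 infusion reaction may allow dosing to resume at the next scheduled dose, and SAP 4.6 uses the date on which stopping was decided. This stands: the Day 1 figures are the extreme case, and the effect shrinks with a later decision.

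Third, other provisions remain. Events that cause stopping are followed to resolution or stabilization, or to the EOSV (12.2.4.4), SAEs are followed to resolution (12.2.2), extra labs are allowed, Table 11 permits extra PK, ADA and cytokine samples after an infusion reaction, and participants are told to report symptoms. A reader might infer from the schedule alone that stoppers go unmonitored; these provisions rule that out. They are, however, discretionary, participant-initiated or without fixed days.

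Fourth, continuing participants also have no scheduled safety labs on Days 2-14, so the laboratory loss inside the window is one draw, at Day 15. That is correct.

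Fifth, the summaries are descriptive, and Part 1B already samples the first dose of the same combination. This limits the harm to first-dose knowledge but does not help Part 2's own DLT count or its multiple-dose data.

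**Conclusion.** The point holds for scheduled assessments. Followed literally, 4.6 leaves a participant stopped on Day 1 with no scheduled visit on Days 2-14 (0 against 3), 2 instead of 5 cytokine/T-cell rows after dose 1, 1 instead of 3 on-study ADA samples, and no scheduled chemistry for about 30-49 days. A stop following dose 2 loses the Day 29 content only.

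Three stronger readings are not supported.

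- A reader might infer that contact at Day 15, or at Day 29 after dose 2, disappears. It does not: Visit 7 falls there, and only the content of Visit 5 or 6 is lost.
- A reader might leave the EOSV on Day 78 and compute a 77-day wait for chemistry (78 - 1). Section 4.1 ties the EOSV to the last dose, so the upper end is about 49 days.
- A reader might size the problem by the chance of any DLT among six. That is not the chance of stopping before Visit 5, which the documents do not give, so no frequency is claimed here.

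The figures assume a stop decided on the day of the last dose, unchanged spacing of Visits 8-10, and that the 1 h and 4 h samples are taken. The change is worth making because it is cheap and protects the primary safety objective. It does not invalidate the design.

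**What to change.** Reconcile Protocol 4.6 with the DLT period in 4.3 and with Tables 8 and 11. State that, when study drug is stopped in Part 2, the post-dose safety labs and the cytokine, T-cell, PK and ADA samples already listed for a dose that was given are still collected, without infusion, before Visits 7-9 or merged with them. For a Day 1 stop, this concerns the Day 2, 4 and 8 items and the pre-dose Day 15 content, the last of which can be taken at Visit 7. For a stop following dose 2, it concerns the Day 29 labs and pre-dose samples, which can also be taken at Visit 7.

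The cost is one sentence in 4.6, a footnote to Tables 8 and 11, and a few already-listed visits or draws for the few participants who stop early. No new type of assessment is needed, and no change to dosing, stopping or treatment rules is proposed.
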